#### 10.1.2. Quarterly Visit Procedures

- Measure vital signs (blood pressure, heart rate, respiratory rate, and oral body temperature).
- Measure height, body weight and head circumference; calculate BMI and BSA.
- For females, re-assess childbearing potential and menstrual history.
- Perform physical examination.
- Obtain a 12-lead ECG.
- Review concomitant medications, documenting any changes since the previous study visit. Medications prescribed on a prn (as needed) basis should be recorded in the eCRF only if actually taken during the study, with defined start and stop dates of dosing.
- Record adverse events experienced, or changes to those already reported, since the previous study visit. Complete the Adverse Events Checklist (Section 15.5)
- Perform the assessments associated with each subject's two preeminent symptoms. (These assessments are specified in the Schedule of Events and Section 6.3.2 Secondary Endpoints).
- Determine subject's current RP103 dose. Administer RP103 dose according to the instructions provided in Section 15.4
- Collect empty and partially empty bottles of RP103. Dispense more RP103 for home administration. Remind the subject and/or caregivers of RP103 dosing instructions.
- Collect blood samples for laboratory tests, within 30 minutes before/after RP103 dose
- Collect breath samples for hydrogen sulfide testing.
- Administer age-specific NPMDS
- Collect (or print from [www.seizuretracker.com](http://www.seizuretracker.com) website) and review seizure activity since the previous clinic visit. Dispense a new paper seizure diary if applicable.
- Collect and review the completed IP diary with the subject and/or caregivers, making corrections as needed. Investigator staff and the subject/caregiver will sign/date the diary as indication of its review and accuracy; dispense a blank diary for subjects to complete until the next study visit.
- Schedule or confirm the next study visit.

#### 10.1.3. Study Exit Visit Procedures

- Measure vital signs (blood pressure, heart rate, respiratory rate, and oral body temperature).
- Measure height, body weight and head circumference; calculate BMI and BSA.
- For females, re-assess childbearing potential and menstrual history.
- Perform physical examination.
- Obtain a 12-lead ECG.
- Review concomitant medications, documenting any changes since the previous study visit. Medications prescribed on a prn (as needed) basis should be recorded in the

eCRF only if actually taken during the study, with defined start and stop dates of dosing.

- Record adverse events experienced, or changes to those already reported, since the previous study visit. Complete the Adverse Events Checklist (Section 15.5)
- Administer age-specific NPMDS
- Perform the assessments associated with each subject's two preeminent symptoms. (These assessments are specified in the Schedule of Events and Section 6.3.2 Secondary Endpoints).
- Determine subject's current RP103 dose. Administer RP103 dose according to the instructions provided in Section 15.4
- Collect empty and partially empty bottles of RP103.
- Collect blood samples for laboratory tests, within 30 minutes before/after RP103 dose
- Collect breath samples for hydrogen sulfide testing.
- Collect and review seizure activity since the previous clinic visit.
- Collect and review the completed diary with the subject and/or caregivers, making corrections as needed. Investigator staff and the subject/caregiver will sign/date the diary as indication of its review and accuracy; dispense a blank diary for subjects.

## **10.2. Fasting, Diet, Fluid and Activity Control**

RP103 will be administered with an acceptable food or liquid and according to the instructions provided in Section 15.4.

## **10.3. Contraception and Hormone Therapy**

### **10.3.1. Women**

If the patient is a female, she will be asked about her menstrual cycle history (including date of last period; menses regularity; typical duration and normalcy; any abnormal discharges; and excessive bleeding).

If she is of childbearing potential and is sexually active, she must be non-lactating and have a negative serum pregnancy test at Screening and Day 1/Baseline and use two of the following acceptable methods of contraception until study termination:

- a) Hormonal contraceptive: birth control pills, injection, patch, vaginal ring or implant;
- b) Condom or diaphragm, with spermicide;
- c) Intrauterine device (IUD);
- d) Sterile male partner (vasectomy performed at least 6 months prior to the study).

### **10.3.2. Men**

If the Subject is a man who has not had a vasectomy, he and his female partner will be asked to practice appropriate contraception, as described above, during the study.

#### 10.4. Clinical Laboratory Evaluations

Clinical laboratory (chemistry, hematology, urinalysis, serum pregnancy), pharmacokinetic and pharmacodynamic biomarker sample analysis will be performed by a central laboratory. **Table 2** summarizes the tests that will be performed.

The Investigator or medically qualified delegate will review the laboratory test findings and assess in writing whether any abnormal result (outside normal reference range) is clinically significant, i.e. associated with an adverse event and not the pre-existing medical history. In such cases, the associated adverse event must be detailed in source documentation and transcribed into the electronic Case Report Form (eCRF).

**Table 2: Clinical Laboratory Tests**

Hematology	Serum Chemistry	Urinalysis
Hematocrit	Alanine aminotransferase	Bilirubin
Hemoglobin	Albumin	Blood (qualitative)
Mean corpuscular hemoglobin	Aspartate aminotransferase	Color
Mean corpuscular hemoglobin concentration	Alkaline phosphatase	Glucose
Mean corpuscular volume	Amylase	Ketones
Erythrocytes	Conjugated bilirubin	Leukocyte esterase
Red cell distribution width	Total bilirubin	Nitrite
Platelet count	Blood urea nitrogen	pH
Differential (absolute, %)	Calcium	Protein
Leukocytes	Bicarbonate	Specific gravity
Basophils	Chloride	Turbidity
Eosinophils	Creatinine	Urobilinogen
Lymphocytes	Gamma glutamyl transpeptidase	Microscopic examination
Monocytes	Glucose	
Neutrophils	Lactate dehydrogenase	
Reticulocyte count*	Phosphorus	
	Potassium	
	Total protein	
	Sodium	
	Uric acid	
	Uric acid	
Other Laboratory Tests		
Serum pregnancy test (human chorionic gonadotropin)		
Pharmacokinetics: Plasma Cysteamine		
Pharmacodynamic Biomarkers: glutathione, glutathione disulfide, lactate		

#### 10.5. Blood Volume

Assuming participation of the entire 24 months study, the estimated volume of blood drawn (in mL) per subject is provided below. If the Investigator suspects alcohol or drug abuse, or deems that additional lab tests are required for the follow-up of an adverse event, more blood samples may be collected.

Study Visit	Maximum # Visits	Chemistry & Hematology	PK	PD	Pregnancy	TOTAL without pregnancy tests	TOTAL with pregnancy tests
Day1 Visit	0 mL (blood was collected at previous Study RP103-MITO-001 Study Exit Visit)						
Quarterly Visit	7	4.5 mL	2 mL	4 mL	0.5 mL	73.5 mL	77 mL
Study Exit Visit	1	4.5 mL	2 mL	4 mL	0.5 mL	10.5 mL	11 mL
						84 mL	88 mL

#### 10.6. 12-Lead Electrocardiograms

Standard 12-lead ECGs will be used for the ECG evaluation. All scheduled ECGs should be performed after the subject has rested quietly in the supine position for at least 5 minutes. A single, 10-second, 12-lead ECG will be obtained at the frequency specified in the Schedule of Events. All ECGs will be retained as a paper copy in the subject's source records. The ECGs will be recorded at the specified timepoints at a speed of 25 mm/sec and amplitude of 10 mm/mV.

The Investigator or medically qualified delegate will review the ECG tracings and assess in writing whether any abnormal result is clinically significant, i.e. associated with an adverse event and not the pre-existing medical history. In such cases, the associated adverse event must be detailed in source documentation and transcribed into the electronic Case Report Form (eCRF).

#### 10.7. Physical Examinations

Physical examinations will be performed by the Investigator or medically qualified delegate at the frequency specified in the Schedule of Events. The physical examination will include assessments of general appearance, eyes, ears, nose and throat, chest (heart, lungs), abdomen (palpation, gastrointestinal sounds), extremities and skin. The exam will also include a basic neurological examination.

#### 10.8. Vital Signs

Vital signs (systolic/diastolic blood pressure, heart rate, respiratory rate, and oral body temperature) will be measured according to the Schedule of Events. Blood pressure will be measured with the arm supported at the level of the heart, and recorded to the nearest 1 mm Hg. The subject should be at rest for at least 5 minutes before the blood pressure is measured.—Screening blood pressure may be retested 3 times at intervals of at least 5 minutes between each measurement. The use of automated devices for measuring blood pressure and heart rate are acceptable. When done manually, heart rate will be measured in the brachial or radial artery for at least 30 seconds.

Head circumference measurement should be taken with a device that cannot be stretched, such as a flexible metal tape measure. Wrap the tape snugly around the widest possible circumference, from the most prominent part of the forehead (often 1-2 fingers above the eyebrow) around to the widest part of the back of the head. Try to find the widest way around the head. Re-measure 3 times, and take the largest number.

#### **10.9. Adverse Event Inquiries**

The active ingredient in RP103 (cysteamine bitartrate) has been associated with CNS symptoms such as seizures, lethargy, somnolence, depression and encephalopathy which are common in this patient population. At each study visit subjects will be queried about the occurrence of these specific symptoms since the previous visit using the Adverse Events Checklist provided in Section 15.5.

In addition, spontaneous adverse event reports will be identified initially by an open-ended, nondirective question.

#### **10.10. Safety Review**

Safety review of all adverse events will be performed periodically by the Investigator. Particular attention will be paid to potential CNS symptoms reported during the study. The investigator will assess such AEs for relationship to underlying disease versus relationship to study drug and determine appropriate action(s) to be taken.

#### **10.11. Newcastle Paediatric Mitochondrial Disease Scale (NPMDS)**

The NPMDS has been introduced to allow evaluation of the progression of mitochondrial disease in patients less than 18 years of age. (The Newcastle Mitochondrial Disease Scale (NMD) provides a similar assessment tool for adult patients). In the paediatric population, demonstrating a genetic or biochemical basis for mitochondrial disease can be very difficult. Consequently we would recommend that the scale be administered to patients where there is a strong clinical suspicion of mitochondrial disease as well as those with a confirmed (biochemical or genetic) diagnosis. Repeated administration of the scale permits the longitudinal monitoring of these patients.

The aim of these disease rating scales is to standardize patient assessment and ensure accurate data collection. This information will provide an invaluable resource to help us understand the natural history of mitochondrial disease in children. It is predicted that the scale will also prove to be a useful tool for future clinical assessment of proposed treatments.

The rating scale encompasses all aspects of mitochondrial disease by exploring several domains: Current Function; System Specific Involvement; Current Clinical Assessment and Quality of Life. Almost every question in the scale has a possible score from 0-3: 0 representing normal, 1- mild, 2- moderate and 3- severe. In each case, examples of mild, moderate and severe impairment or disability are given.

There are three age-specific versions of the NPMDS, 0-24 months, 2-11 years and 12-18 years.

#### **10.12. Investigational Product Accountability**

Cysteamine Bitartrate Delayed-release Capsules (RP103) will be supplied by the Sponsor or its representative. The Investigational Pharmacy will record the lot numbers. Accountability will be performed on the clinical trial supply. The Investigator or a designee will verify and acknowledge receipt of the RP103 by signing and returning all required forms. All medication must be stored in a secured area under the proper storage

requirements with access restricted to the Investigator or designees. Medication designated for this clinical study must not be administered to any subjects other than those enrolled in this specific investigation and may not be used for any laboratory or animal research. All medication dispensed to subjects must be properly labeled and accurately recorded on the drug accountability records maintained at the pharmacy. A copy of this record must be returned to the Sponsor or its designee on completion of the study for accountability purposes. A clinical research associate will periodically review the drug accountability during the study. At the end of the study, all unused and expired medication will be retained until disposition of study medication has been made by the Sponsor or its designee.

## 11. ASSESSMENT OF SAFETY

### 11.1. Definition and Grading Intensity of Adverse Events/Experiences

An adverse event/experience (AE) is defined as any untoward medical occurrence in a patient or clinical investigation subject administered a pharmaceutical product and which does not necessarily have a causal relationship with this treatment. An adverse event can therefore be any unfavorable and unintended sign (including an abnormal laboratory finding), symptom, or disease temporarily associated with the use of a medicinal (investigational) product, whether or not related to the medicinal (investigational) product. A treatment emergent adverse event is an AE that is reported after a dose of study drug.

Adverse events/experiences comprise all disturbances of general health status, subjective and objective disease symptoms (including laboratory abnormalities), and accidents observed in the context of a clinical trial, irrespective of a possible causal relationship with the administration of the trial substance. Events occurring in the framework of a clinical trial during drug-free, and post-treatment periods, or in a reference group receiving drug therapy, are also to be designated as AEs.

All AEs, whether volunteered, elicited, or noted on physical examination, will be recorded throughout the study.

Where possible, the severity of AEs will be categorized Common Terminology Criteria for Adverse Events (CTCAE), Version 3.0 [Cancer Therapy Evaluation Program, 2003] or otherwise as follows:

- **MILD (Grade 1):** experience is minor and does not cause significant discomfort to subject or change in activities of daily living (ADL); subject is aware of symptoms but symptoms are easily tolerated.
- **MODERATE (Grade 2):** experience is an inconvenience or concern to the subject and causes interference with ADL, but the subject is able to continue with ADL.
- **SEVERE (Grade 3):** experience significantly interferes with ADL and the subject is incapacitated and/or unable to continue with ADL.
- **LIFE THREATENING (Grade 4):** experience that, in the view of the Investigator, places the subject at immediate risk of death from the event as it occurred (i.e., it does not include an event that had it occurred in a more severe form, might have caused death).
- By the CTCAE criteria defined above, the Grade 5 category is death.

### 11.2. Stopping Criteria

Close monitoring of the patients during the study will be performed. Any decision to stop the clinical trial will be immediately communicated to all Investigators and to the United States FDA and competent authorities of any other participating countries.

*Stopping Criteria (continued)*

**Individual patient dosing will be stopped if:**

- A patient exhibits a treatment-emergent adverse event of Common Terminology Criteria for Adverse Events (CTCAE) Grade 3 or higher and not likely related to the underlying disease, and possibly, probably or definitely related to study drug.

**A patient will be discontinued if they exhibit an:**

- Unexplained fever ( $> 38.5^{\circ}\text{C}$ ) for  $> 24$  hours.

**The study will be halted and FDA will be consulted if:**

- Two or more patients develop the same CTCAE Grade 3 adverse event;
- One patient develops a CTCAE Grade 4 adverse event;
- One or more unexpected drug-related deaths\*.
- Onset of one or more drug-related cases of:
  - Heart failure (NYHA Class II or greater);
  - Respiratory failure (Type 1 or Type 2);
  - Acute liver failure (associated with an international normalized ratio (INR) of greater than 1.5, and any degree of mental alteration (encephalopathy) in a patient without preexisting cirrhosis);
  - Malignant hypertension (i.e., Diastolic blood pressure  $> 140$  mmHg);
  - Nephrotic syndrome which includes protein in the urine (more than 3.5 grams per day) and one or more of the following clinically significant symptoms: low blood protein levels and/or high cholesterol levels and/or high triglyceride levels and/or edema.

\* Any death is an SAE by definition and must be reported to the Sponsor or Sponsor's representative designated to receive SAE reports. Whether or not the event or any other SAE is expected or unexpected will be assessed by Sponsor or its representative according to a pre-specified Safety Monitoring Plan (i.e., the current RP103 Investigator Brochure will be used as reference). It is the Sponsor or its representative's responsibility to make this assessment and to generate and distribute/submit any expedited regulatory reports as appropriate, e.g. IND Safety Reports and SUSARs.

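### Death is the only one of eight study-halt triggers with an expectedness condition, so a drug-related death classed as expected can leave the study running

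*Protocol*

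**What the plan says.** The study-level part of Protocol 11.2 has two grade-based triggers, one for death and five for named organ events.

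- Grade-based: the same Grade 3 event in at least two patients, or "One patient develops a CTCAE Grade 4 adverse event". Neither mentions relatedness or expectedness.
- Death: "One or more unexpected drug-related deaths". Both conditions must be met.
- Organ events: "Onset of one or more drug-related cases of" five conditions, the first being "Heart failure (NYHA Class II or greater"). Relatedness is required; expectedness is not.

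A footnote to the death trigger says who decides: "Whether or not the event or any other SAE is expected or unexpected will be assessed by Sponsor or its representative". It adds that "the current RP103 Investigator Brochure will be used as reference". The same footnote links this judgement to expedited regulatory reports.

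Two other places bear on how the list is read. Protocol 11.1 defines Grade 4 as an event that "places the subject at immediate risk of death from the event as it occurred" and makes death a separate category, Grade 5. The individual dosing rule in Protocol 11.2 applies to events of "Grade 3 or higher and not likely related to the underlying disease" that are at least possibly related to study drug. SAP 2.3 repeats the halt list, including the qualifier on death.

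**The concern.** The ordering is inverted. The worst outcome on the list faces the strictest test, while non-fatal NYHA Class II heart failure judged drug-related halts the study whether or not it was foreseen. Expectedness serves expedited reporting; it does not tell anyone whether it is safe to go on dosing the other children.

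At stake is a death that is sudden, or recorded directly as Grade 5, and judged drug-related. If the sponsor classes it as expected, nothing in the plan obliges a halt. The individual dosing rule covers only the affected patient, so it does nothing for the others across the four sites.

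Some of the remaining safeguards use the same classification. Protocol 11.4 ties the stated IRB/EC notice to SAEs needing an expedited IND safety report, and Protocol 13.4 has the IRB/EC told of serious events that are also unexpected. Safety review in Protocol 10.10 is periodic and done by the investigator, and the documents describe no independent monitoring committee.

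**Working it through.** The plan gives no figure on this point, so the check is a count and a logical test of each trigger, taken from Protocol 11.2 with the grade definitions in 11.1.

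| # | Halt trigger | Must be drug-related? | Must be unexpected? |
|---|---|---|---|
| 1 | Same Grade 3 event, two or more patients | No | No |
| 2 | One Grade 4 event | No | No |
| 3 | Death | Yes | **Yes** |
| 4 | Heart failure | Yes | No |
| 5 | Respiratory failure | Yes | No |
| 6 | Acute liver failure | Yes | No |
| 7 | Malignant hypertension | Yes | No |
| 8 | Nephrotic syndrome | Yes | No |

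**Counts.** Triggers: 2 + 1 + 5 = 8. Relatedness required: 1 + 5 = 6 of 8. Expectedness required: 1 of 8.

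**Test case: a drug-related death that the sponsor classes as expected.**

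1. Trigger 3 is not met, because the death is not unexpected.
2. Triggers 4 to 8 are met only if the death arises from one of the five named conditions. Protocol 5.3 lists seizures, encephalopathy, and gastrointestinal ulceration and bleeding among events associated with cysteamine. None of these is by itself one of the five.
3. Trigger 2 is met if the event was recorded as Grade 4 before death. If it was recorded only as Grade 5, the trigger does not clearly apply. It names Grade 4 without adding *or higher*, whereas the individual dosing rule in the same section does add those words. If Grade 4 were read to include Grade 5, every death from any cause would already halt the study and trigger 3 would have no work to do. The reading that gives trigger 3 a purpose leaves the gap open.
4. Trigger 1 is met only if the event is part of a Grade 3 event seen in at least two patients.

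A drug-related death outside triggers 1, 2 and 4 to 8 therefore depends on trigger 3 alone:

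| Sponsor's class | Current wording | With *unexpected* deleted |
|---|---|---|
| Unexpected | Halt | Halt |
| Expected | No mandatory halt | Halt |
| Classes covered | 1 of 2 | 2 of 2 |

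After the deletion, 0 of 8 triggers depend on expectedness. These counts describe what the rule covers. They are not frequencies.

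**The case against.** The strongest reply is that the gap may be empty. It opens only if the sponsor classes a drug-related death as expected, and the reference for that is a brochure outside the documents. Protocol 5.3 lists known risks but no fatal outcome, and listing a reaction does not make a death from it expected. If the brochure lists no fatal event, every drug-related death is unexpected and the trigger always fires. This stands as a limit: the defect in the wording is certain, but its practical reach is unknown.

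Second, most fatal courses would be caught elsewhere. A fatal bleed or prolonged seizure would ordinarily pass through a state meeting the Grade 4 definition, and one such event halts the study unconditionally. This also stands, and it leaves a narrow remainder.

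Third, other controls exist. Every death is an SAE, an initial written report is due within 24 hours (Protocol 11.4), and the sponsor, a regulator or an IRB/EC can still choose to stop. These soften the consequence, but none makes a halt mandatory.

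Fourth, moving from 1 of 2 classes to 2 of 2 merely restates the deleted word, and the total of eight depends on counting the five organ events separately. Both are fair comments. The counts show only where the rule has a hole, and death is the only trigger with an expectedness condition however the list is counted.

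**Conclusion.** The concern holds. Of eight halt triggers, death alone requires the event to be unexpected, and no other text in either document requires a halt for an expected drug-related death. The uncovered case must meet all of these conditions: related to study drug, classed as expected, never recorded as Grade 4, not due to a listed organ event, and not part of a repeated Grade 3 event.

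The conclusion rests on two things. One is reading the Grade 4 trigger as not extending to Grade 5, which the contrast with the individual dosing rule supports. The other is that the brochure could class some fatal event as expected, which cannot be checked here. No probability is claimed. The change is worth making because, if no death would be classed as expected, it alters nothing, and if one could be, it closes a gap in the protection of the remaining children.

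**What to change.** Delete *unexpected* from the death trigger in Protocol 11.2 so that any drug-related death, one or more, halts the study. Make the same deletion in SAP 2.3 for consistency. Keep the footnote, since expectedness is still needed for IND Safety Reports and SUSARs.

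Extending the Grade 4 trigger to Grade 4 or higher would also close the gap, but it would halt the study for deaths from the underlying disease as well. That is a choice for the safety team and is not needed here.

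The cost is one word, through the amendment route in Protocol 13.1 with regulatory and IRB/EC approval. The downside is a possible extra pause for FDA consultation after a drug-related death; how often cannot be estimated from the documents. The pause would extend to deaths judged only possibly related if the team reads drug-related that way, as the individual dosing rule and SAP 4.6.2 do. No analysis changes. SAP 1.1 shows that the SAP was written after the study had closed early, so the edit there is for consistency only.

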Based on these preliminary results, Raptor conducted a pilot Phase 2b study, Study RP103-01, to evaluate the safety, tolerability, pharmacokinetics (PK) and pharmacodynamics (PD) of a single dose of RP103 compared to a single dose of Cystagon in 9 patients with cystinosis. Study RP103-01 confirmed that RP103 behaved similar to EC-cysteamine, enteric-coated Cystagon capsules, and therefore, a confirmatory Phase 3 study (RP103-03) was subsequently conducted to determine the efficacy and safety of RP103 compared to Cystagon in patients with nephropathic cystinosis. Study RP103-03 demonstrated that RP103 was non-inferior to Cystagon in maintaining patient WBC cystine levels. Based on results of Study RP103-03, patients were allowed to enroll in Study RP103-04, a long-term safety follow-on study.

For the treatment of cystinosis, the target maintenance dose of PROSYSBI is 1.30 grams/m^2/day administered in two divided doses (one dose every 12 hours (Q12H)). The PROSYSBI dose can be increased to a maximum of 1.95 grams/m^2/day. The dose of 1.95 grams/m^2/day has been associated with an increased rate of withdrawal from treatment with immediate-release cysteamine due to intolerance and an increased incidence of adverse events.

The treatment of inherited mitochondrial diseases with cysteamine is potentially based on different mechanisms of action than that for treatment of cystinosis, although one key biochemical reaction, which is the basis for the treatment of cystinosis, seems to play a significant role also. Cysteamine is an aminothiol that participates in a thiol-disulfide interchange reaction converting cystine into cysteine and cysteine-cysteamine mixed disulfide. This cysteine-cysteamine mixed disulfide can exit the lysosome through the lysosome membrane, as it is transported through the intestinal barrier or the blood brain barrier, by the lysine transporter or a lysine-like transporter, the PQLC2 protein. This biochemical reaction results in an increase of the cellular thiol pool, making more cysteine available for glutathione (GSH) synthesis. Glutathione is composed of the amino acids cysteine, glutamate and glycine. The availability of cysteine, which exists primarily as cystine, is the major rate-limiting factor in GSH production.

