### **5.5. Dose Rationale**

RP103 will be administered at the same doses and following a progressive dose titration as used in patients with cystinosis for ~ 20 years, since this has been associated with better tolerability.

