### **7.3. Study Drug Dosing Methodology**

Upon RP103-MITO-002 study entry, subjects will continue on the last total daily dose of RP103 taken during the previous RP103-MITO-001 study. Subsequent RP103 dose adjustments are permitted (e.g. as the subject grows, or if deemed necessary by the Investigator for tolerability reasons).

The Sponsor's medical officer may be consulted for assistance making RP103 dose adjustment decisions at any time during the study. NOTE: For each subject, when calculating the number of capsules to be taken every 12 hours (i.e. half of the prescribed total daily dose), if rounding is required to get a whole number of capsules to be taken, then rounding should be down and not up.

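### The nephrotic-syndrome study-halt condition uses a fixed 3.5 g/day of urine protein for children from 5 kg, so the trigger is less sensitive in smaller children

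*Protocol*

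**What the plan says.** Protocol section 11.2 lists conditions under which the study is halted and FDA is consulted. One is the onset of a single drug-related case of "Nephrotic syndrome which includes protein in the urine (more than 3.5 grams per day"), together with "one or more of the following clinically significant symptoms: low blood protein levels and/or high cholesterol levels", raised triglycerides or edema. The two parts are joined by "and", so exceeding 3.5 g/day is necessary. SAP section 2.3 repeats the condition. Neither document gives a limit per m², per kg or as a protein/creatinine ratio.

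The population is paediatric (section 6.1), the minimum weight is 5 kg (section 8.1), and the primary scale has a version for 0-24 months (section 10.11).

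Body size is taken into account elsewhere:

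- Section 5.2 gives the cystinosis dose by surface area: "the target maintenance dose of PROSYSBI is 1.30 grams/m"² per day.
- Section 5.5 carries this over: "RP103 will be administered at the same doses and following a progressive dose titration as used in patients with cystinosis".
- Section 7.3 lets the dose change with growth: "Subsequent RP103 dose adjustments are permitted (e.g. as the subject grows").
- Section 10.1.2 has sites "Measure height, body weight and head circumference; calculate BMI and BSA" at each quarterly visit. The Schedule of Events requires the same at Day 1 and Study Exit.

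Other rules in section 11.2 do not use the 3.5 g figure. A child's dosing stops for a treatment-emergent event of "Grade 3 or higher and not likely related to the underlying disease, and possibly, probably or definitely related to study drug". The study also halts if "Two or more patients develop the same CTCAE Grade 3 adverse event", or after one Grade 4 event or an unexpected drug-related death.

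**The concern.** A fixed amount per day is a larger loss, relative to body size, for a small child than for a large adolescent. If protein loss is judged per m², the same rule demands a more severe loss before it fires in a smaller child.

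The accompanying signs do not correct this. Low blood protein is one of them, and albumin and total protein are measured at every visit (Table 2), so a small child can meet that part and still fail the condition because 3.5 g/day is not reached.

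What is at stake is study-level safety. By listing nephrotic syndrome separately, the sponsor made one related case enough to halt, whatever its CTCAE grade. That protection becomes weaker as body size falls. No sample size, error rate or planned analysis is affected.

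**Working it through.** **Inputs from the documents.** The limit is 3.5 g/day (Protocol 11.2, SAP 2.3). The lowest eligible weight is 5 kg (section 8.1). Section 15.1 gives the Haycock formula:

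BSA (m²) = 0.024265 × height(cm)^0.3964 × weight(kg)^0.5378

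**Assumptions.** The documents give no heights and no enrolled weights, so every weight-height pair below is assumed, as is the 70 kg, 170 cm reference. So is the premise that protein loss should be compared per m². The documents give no per-m² equivalent or derivation of the 3.5 g figure, so there is no plan figure to reproduce.

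**Formulas.** The limit per m² is 3.5 / BSA. The ratio to the reference is BSA(70 kg, 170 cm) / BSA(child). The daily loss with the same value per m² as the reference limit is 3.5 × BSA(child) / BSA(70 kg, 170 cm).

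**Two rows in full.**

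- 70 kg, 170 cm: 0.024265 × 7.659 × 9.824 = 1.826 m², and 3.5 / 1.826 = 1.92 g/m²/day.
- 20 kg, 110 cm: 0.024265 × 6.445 × 5.008 = 0.783 m², and 3.5 / 0.783 = 4.47 g/m²/day. The ratio is 1.826 / 0.783 = 2.33.

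| Weight, assumed height | BSA (m²) | 3.5 g/day as g/m²/day | Ratio to 70 kg | Loss equal per m² to the 70 kg limit (g/day) |
|---|---|---|---|---|
| 70 kg, 170 cm | 1.826 | 1.92 | 1.00 | 3.50 |
| 40 kg, 145 cm | 1.269 | 2.76 | 1.44 | 2.43 |
| 30 kg, 132 cm | 1.047 | 3.34 | 1.74 | 2.01 |
| 20 kg, 110 cm | 0.783 | 4.47 | 2.33 | 1.50 |
| 10 kg, 75 cm | 0.464 | 7.55 | 3.94 | 0.89 |
| 5 kg, 58 cm | 0.288 | 12.14 | 6.33 | 0.55 |

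**Sensitivity to height.** With the 70 kg reference varied over 160-180 cm, the ratio is:

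- 1.37-1.49 at 40 kg (140-155 cm)
- 2.20-2.43 at 20 kg (105-120 cm)
- 6.02-6.61 at 5 kg (55-62 cm)

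The reference limit itself runs from 1.87 to 1.96 g/m²/day.

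**Sensitivity to the choice of scale.** Per kg, the limit is 3.5 / 70 = 0.05 g/kg/day at 70 kg and 3.5 / 20 = 0.175 at 20 kg, a 3.5-fold gap. The direction does not depend on choosing BSA, but the size does.

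**Meaning.** At 20 kg, a loss above about 1.5 g/day and up to 3.5 g/day exceeds the 70 kg limit per m² but does not meet the written condition.

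**The case against.** The strongest objection is that the arithmetic shows only that children are smaller. It becomes a fault only if nephrotic-range loss should be judged by body size, and neither document says so. The passages on dose and BSA concern dosing and measurement, not a renal threshold. This stands as a limit on the point: BSA scaling is an assumption, and 1.9 g/m²/day is back-calculated from one assumed subject, so it is not a diagnostic cut-off.

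The gap is also narrow. A Grade 4 event, or the same Grade 3 event in two patients, halts the study whatever the urine protein. A related Grade 3 event stops that child's dosing. Serious events are reported within 24 hours (section 11.4), and the sponsor sends expedited reports as appropriate (footnote to section 11.2). No renal event appears among the reactions in section 5.3 or on the checklist in section 15.5. This narrows the gap but does not close it. The dosing stop protects one child, reporting is not a halt, and with up to 25 subjects planned (Protocol 12.3; the SAP says up to 35) a second matching Grade 3 case may never occur.

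Measurement is a further difficulty. Table 2 lists urinalysis protein but no timed collection, so scheduled tests cannot give g/day at any body size. That is correct, but the present limit already depends on for-cause testing, and a scaled limit depends on it equally.

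A reader might infer that the halt turns on the child's size and not on severity. The documents do not support that reading: the condition depends on both. On the assumed heights, a 20 kg child losing more than about 4.5 g/m²/day still meets the urine-protein part.

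**Conclusion.** The point holds as a loss of sensitivity. The fixed limit is about 1.4 times higher per m² at 40 kg, 2.3 times at 20 kg and 6.3 times at 5 kg than at 70 kg and 170 cm. The case that can be missed is a single drug-related one with an accompanying sign, below 3.5 g/day, below Grade 4 and not repeated.

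This rests on assumed heights, an assumed 70 kg reference and BSA as the scale. A reader might infer that an enrolled child was left unprotected. The documents cannot show that, because they give neither the enrolled weights nor the CTCAE grade that such a case would receive, and no child near 5 kg is known to have entered.

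The sponsor closed the study early (SAP 1.1), so the point bears on the protocol text and any reuse of it. Severity is minor.

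**What to change.** In Protocol 11.2 and SAP 2.3, replace the fixed 3.5 g/day with a limit per m², using BSA from the most recent visit, set at no more than about 1.9 g/m²/day. That value keeps the present limit at 70 kg and 170 cm. The sponsor's medical officer should confirm the paediatric cut-off. The rest of the condition can stay as written.

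The urine value would come from for-cause testing, as it must now; stating this in the text would help. A spot protein/creatinine limit is not a free substitute: Table 2 lists creatinine only under serum chemistry, so that option would need an added urine creatinine and should otherwise be left out.

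The cost is one wording edit in each document, with no new visit, scheduled sample or analysis. The downside is that the study could halt at a lower absolute loss in a small child, for example about 1.5 g/day at 20 kg, which is why the cut-off needs clinical confirmation.
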